
Rationale and Purpose: In December 2019, a group of pneumonia cases was reported at a wholesale seafood market in Wuhan in the Hubei province of China. The disease, which has subsequently become known as COVID-19, was found to be caused by a previously unknown coronavirus since named severe acute respiratory syndrome coronavirus 2 (SARS-CoV-2). The first detected case of COVID-19 in South Africa was on 5th March 2020. The global and local pandemic that followed the initial outbreak has already resulted in a significant number of cases and deaths, as well as major and long-term economic, social and health sector damage. In countries that have already been severely affected, cross-sectional screening of the general population indicates that we are far from reaching “herd immunity” in those populations. There is therefore an urgent and unmet need for identification of therapies for treating COVID-19 disease and vaccines for preventing the disease. These interventions are essential to reducing morbidity and mortality and returning to a form of social and economic normalcy.
 
Human adenovirus type 5 (hAd5) is an attractive vector for vaccine development against COVID-19 because it can be readily produced at scale and has a history of safe clinical use in a vaccine setting. However, the utility of first-generation hAd5 vectors is increasingly constrained due to widespread prevalence of adenoviral (i.e. vector) immunity in the general population. A phase 1 trial of an Ad5 candidate vaccine against SARS-CoV-2 in Wuhan has already demonstrated that there is a negative impact on immunogenicity in those with high Ad5 neutralising antibodies at baseline.
 
The prior demonstration of an increased risk for HIV-1 acquisition in men who received a hAd5 vectored HIV vaccine, thought to be related to hAd5 vector induced immune responses, also needs to be considered when developing and testing a vaccine that needs inclusion of high HIV prevalence settings, such as a COVID-19 vaccine.
 
To address the urgent need for a scalable, safe vaccine that can overcome the limitations of first-generation hAd5 vaccines a 2nd generation oncology hAd5 platform has been leveraged to

create a vaccine containing SARS-CoV-2 spike (S) and nucleocapsid(N) antigens. The 2nd generation hAd5 platform has already demonstrated safety and efficacy in 125 patients in 13 clinical trials including at the National Cancer Institute.

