Immunogenicity: To determine cellular and mucosal immunogenicity of hAd5-S-Fusion+N-ETSD. To assess for any induction or enhancement of Ad5 immune response by the Ad5 vector in hAd5-S-Fusion+N-ETSD.	Immunogenicity: Timing per Schedule of Events 
 • T cell activity against SARS-CoV-2 S, RBD and N protein • Mucosal Immunogenicity as assessed by GMT of IgA antibody levels to SARS CoV-2 S protein, RBD and N protein • T cell activity and IgG titres against Ad5, comparing baseline to day 29 and day 181 and 202(in cohorts 3, 4, 5, 6 and cohorts 1 and 2 respectively)

Study Design:

This is a phase 1b, open-label study in adult healthy participants. This clinical trial is designed to assess the safety, reactogenicity, and immunogenicity of the hAd5-S-Fusion+N-ETSD vaccine and select a dose for future studies. The hAd5-S-Fusion+N-ETSD vaccine is a hAd5 [E1-, E2b-, E3-] vector-based targeting vaccine encoding the SARS-CoV-2 S and N proteins. The hAd5-S-Fusion+N-ETSD vaccine is designed to induce both humoral and cellular responses even in individuals with pre-existing adenoviral immunity. Thus, the potential exists for the hAd5-S-Fusion+N-ETSD to induce SARS-CoV-2 immunity and prevent or lessen the health impact of COVID-19 infection in healthy participants. Up to 60 healthy participants will be divided into 6 cohorts:

Study Cohorts, Dosing Schedules, Mode of Administration and Dose of hAd5-S-Fusion+N-ETSD

Cohort	Number of participants	Dosing Schedule	Mode of Administration	Dose
1	10	Day 1	SC	5×10^{10} VP
		Day 22	SC	5×10^{10} VP
2	10	Day 1	SC	1×10^{11} VP*
		Day 22	SC	1×10^{11} VP*
3	10	Day 1	SC	1×10^{11} VP*
4	10	Day 1	SL	1×10^{11} VP
5	10	Day 1	SC	1×10^{11} VP*
			and SL	1×10^{11} VP
6	10	Day 1	IN	2×10^{10} VP into each nostril**

SC= subcutaneous; SL= sublingual; IN= intranasal; VP= viral particles; * In the event of safety concerns participants will be dosed at 5×10^{10} VP/dose; ** Total IN dose is given is 4×10^{10} VP as vaccine will be administered into both nostrils

Cohort 1-2 enrolled participants who were SARS-CoV-2 antibody serology negative. For cohorts 3-6, only participants who are SARS-CoV-2 antibody serology positive will be enrolled to evaluate boosting of pre-existing SARS-CoV-2 immune responses and compare the effect of route of administration on the efficacy (and magnitude thereof), reactogenicity and safety of the boosting effect.

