
Evaluation of Endpoints:
 
Safety: Safety endpoints include assessments of treatment-emergent MAAEs, SAEs, solicited local and systemic reactogenicity AEs, unsolicited AEs, safety laboratory tests, HIV testing and vital signs. Toxicities will be graded using the Guidance for Industry: Toxicity Grading Scale for Healthy Adult and Adolescent Volunteers Enrolled in Preventive Vaccine Clinical Trials (2007).
 
Immunogenicity: GMT of S-specific and N specific antibodies against 2019 novel coronavirus, GMT of neutralizing antibody, and GMT of IgA antibody levels will be evaluated. T cell activity against SARS-CoV-2 S, RBD and N protein will be measured by standard immune assays. Humoral and cellular immunity against the Ad5 vector will be measured at baseline, day 29 and day 181 and 202 (in cohorts 3, 4, 5, 6 and cohorts 1 and 2 respectively) to assess for any induction or enhancement of Ad5 immune responses.
	
Statistical Methods:
 
The purpose of this study is to determine the safety, reactogenicity, and immunogenicity of hAd5-S-Fusion+N-ETSD and select an optimal dose and formulation for future studies. Descriptive statistics will be presented for all study endpoints by individual cohort, pooled by dose level, and for all cohorts combined.
 
Safety will be assessed by the incidence of treatment-emergent MAAEs, SAEs, and solicited local and systemic reactogenicity AEs, and unsolicited AEs for the time period of interest, overall and by grade using the Guidance for Industry: Toxicity Grading Scale for Healthy Adult and Adolescent Volunteers Enrolled in Preventive Vaccine Clinical Trials (2007). Clinically significant changes in safety laboratory tests and vital signs also will be summarized. As suggested by the Ad5 literature and expert opinion, participants will be monitored for incident HIV infection during the follow up period .
 
Immunology analyses will be used to provide an assessment of immune responses. GMFRs and GMTs and their associated 95% confidence intervals (CIs) will be computed by exponentiation of the corresponding log-transformed means and 95% CIs. The percentage of participants who seroconverted (as defined as 4-fold change in antibody titer relative to baseline) and 95% Clopper-Pearson CI will be summarized. Neutralizing antibody levels and CD8+ and CD4+ T-Cell activity also will be summarized.

Figure 1: Study Schema

* In the event of safety concerns participants will be dosed at 5×10^{10} VP/dose

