^a Day 1 chemistry, haematology, and urinalysis assessments do not need to be repeated if screening assessments were performed within 7 days prior to the first study vaccination; ^b Height required at screening visit only; ^c Vital signs of temperature, heart rate, blood pressure, and respiratory rate will be assessed at every visit. Temperature will be documented at each visit and subsequently if clinically indicated; ^d See Table 12 or additional details on laboratory assessments. Blood draws for lab assessments at vaccination visits should occur prior to vaccine administration; ^e Haematology to include FBC with differential (5 part) as outlined in Table 12. Blood draws for lab assessments at vaccination visits should occur prior to vaccine administration; ^f Urinalysis testing will include at a minimum protein, glucose, and presence of red blood cells. Sample collection at vaccination visits should occur prior to vaccine administration; ^g Immunogenicity testing includes measures of antibody response and cell-mediated immunity against target antigens, as well as hAd5 serostatus for determining baseline, day 29 and day 181 and 202(in cohorts 3, 4, 5, 6 and cohorts 1 and 2 respectively) hAd5 immunity and monitoring for anti-vector immune responses. Sample collection at vaccination visits should occur prior to vaccine administration.

^h Serum or urine pregnancy tests for females of child-bearing potential at baseline/screening and each visit where study drug is administered, and at 30 days post last dose of vaccine; ⁱ Complete physical exam at screening visit. A routine symptom directed physical exam at subsequent visits; ^j Assessment of reactogenicity AEs includes a baseline assessment of the injection site and any signs or symptoms that may overlap with reactogenicity, as well as an assessment of immediate reactogenicity AEs 30 minutes after vaccine administration; ^k HIV pre- and post-test counselling are done at each visits where blood is taken for HIV testing; ^l Tuberculosis Screening per local guidelines

☺ = In-person visit; ☎ = Telephonic follow-up

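### The exploratory Ad5 objective joins induction and enhancement, but no planned summary splits participants by the baseline Ad5 serostatus that is already measured

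*Combined protocol and SAP*

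**What the plan says.** The synopsis sets a single exploratory objective for anti-vector immunity: "To assess for any induction or enhancement of Ad5 immune response by the Ad5 vector in hAd5-S-Fusion+N-ETSD". The matching endpoint is "T cell activity and IgG titres against Ad5, comparing baseline to day 29 and day 181 and 202", the last two days applying to Cohorts 3-6 and Cohorts 1-2 respectively. Neither induction nor enhancement is defined, and no Ad5 responder threshold is given.

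Under Statistical Methods, the groupings are fixed for everything: "Descriptive statistics will be presented for all study endpoints by individual cohort, pooled by dose level, and for all cohorts combined". Titre summaries are described in general terms: GMFRs and geometric mean titres (GMTs) "will be computed by exponentiation of the corresponding log-transformed means and 95% CIs". A fourfold responder percentage is also described ("The percentage of participants who seroconverted (as defined as 4-fold change in antibody titer relative to baseline) and 95% Clopper-Pearson CI will be summarized"), but the primary endpoint list attaches seroconversion to the SARS-CoV-2 and neutralising-antibody endpoints. No sentence says which statistic applies to Ad5.

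Footnote g to the Schedule of Events says that immunogenicity testing includes antibody and cellular responses to the target antigens "as well as hAd5 serostatus for determining baseline, day 29 and day 181 and 202". Baseline Ad5 status will therefore be known, but no listed analysis uses it. No eligibility criterion mentions Ad5 status, so people with and without prior Ad5 immunity can enter.

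The Rationale refers to "widespread prevalence of adenoviral (i.e. vector) immunity in the general population" and gives no percentage. It also reports, from an earlier Ad5 vaccine trial, that "there is a negative impact on immunogenicity in those with high Ad5 neutralising antibodies at baseline".

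**The concern.** The two halves of the objective concern different people. Someone with no Ad5 immunity on Day 1 can acquire it. Someone who already has it can only have it raised or left alone. A summary over both groups averages two distinct responses, with weights set by whoever happened to enrol. If the Rationale is right that vector immunity is common, the Ad5-positive group is probably the larger and will dominate the average.

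The endpoint has some importance. The Rationale argues that the E2b-deleted vector provokes little response to Ad5 proteins, and that this is what makes testing feasible where HIV prevalence is high. The Ad5 comparison is the trial's direct look at that claim. Ad5-negative participants are the ones in whom new vector immunity could appear, and the planned groupings do not isolate them.

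**Working it through.** **Inputs from the documents.** Six cohorts of 10, up to 60 participants; summaries by cohort, by dose level and overall; log-scale means for titres. The plan gives no Ad5 prevalence, fold rise, SD or precision target, so there is no figure of its own to reproduce.

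**Assumptions.** Fold rise F = 16 in Ad5-negatives; E = 1 (no change) in Ad5-positives; SD of log10 fold rise 0.25 within each group; Ad5-positive share p of 50% to 90%; GMFR as the Ad5 statistic.

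**Step 1: dilution.** A geometric mean averages logs, so the expected pooled GMFR = F^(1-p) × E^p. With E = 1:

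- p = 50%: 16^0.5 = 4.0
- p = 70%: 16^0.3 = 2.3
- p = 80%: 16^0.2 = 1.74
- p = 90%: 16^0.1 = 1.32

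**Step 2: what the unsplit interval shows.** Each participant is Ad5-negative with probability 1-p, and a 95% t-interval is formed on the log10 fold rise. Simulated percentage of intervals that exclude 1:

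| Ad5-positive | n = 10 (one cohort) | n = 20 | n = 60 (all combined) |
|---|---|---|---|
| 50% | 72% | 99% | 100% |
| 70% | 31% | 74% | 99.9% |
| 80% | 14% | 43% | 96% |
| 90% | 5% | 14% | 55% |

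These figures let the number of negatives vary by chance. Fixing it at 2 of 10 gives about 5% instead of 14%; fixing it at 12 of 60 gives over 99% instead of 96%. The message is the same.

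**Step 3: detection is not interpretation.** With 12 negatives among 60, the overall GMFR is 1.74 with a typical 95% CI of 1.26 to 2.41. A 1.74-fold rise in all 60 would give the same point estimate. A responder percentage has a similar limit. If every negative and no positive rises fourfold, the unsplit result is 12/60 = 20% (Clopper-Pearson 10.8% to 32.3%). Split by baseline status it is 12/12 (73.5% to 100%) against 0/48 (0% to 7.4%).

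**Step 4: precision of a split.** The interval for k negatives is 16 multiplied and divided by 10^(t × 0.25/√k), with t the 97.5% point on k-1 degrees of freedom. At 80% positive, Cohorts 1-2 (20 people) have about 4 negatives, Cohorts 3-6 (40 people) about 8, and all cohorts about 12:

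- k = 4: factor 2.50, CI 6.4 to 40
- k = 8: factor 1.62, CI 9.9 to 26
- k = 12: factor 1.44, CI 11 to 23

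Within one cohort of 10 the split is too thin for intervals: 2/2 responders has a CI of 15.8% to 100%. At 80% positive, the chance that a cohort has no Ad5-negative at all is 0.8^10 = 11%.

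**The case against.** The plan already includes an all-cohort summary. Under the assumptions above it shows a rise in most settings, failing often only when about 90% are Ad5-positive. That stands. A reader might infer that strong induction would be averaged out of sight; the planned combined summary does not support that reading.

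The inputs are also open to challenge. Widespread immunity is not a percentage, and at 50% positive even a single cohort has an expected GMFR of 4.0. Nothing in the documents says that Ad5-positive participants have little room to rise; the objective itself contemplates enhancement. With 1.5-fold enhancement in positives, a cohort of 10 at 80% positive excludes 1 in about 65% of simulated trials. This also stands, although that average still mixes the two responses.

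Nor does the plan commit to GMFR for Ad5. A responder percentage, the later serostatus results or the spread of the data could reveal a subgroup that rose: at 80% positive, about 90% of simulated cohorts of 10 contain at least one fourfold rise, and the median SD is 0.54 against 0.25 within groups. This is fair, but no text commits to tabulating any of these by baseline status.

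Finally, the endpoint is exploratory and descriptive, and no decision rule hangs on it. Incident HIV is followed directly as a secondary endpoint through 12 months. A reader might infer that a flat average would be declared proof of no vector immunity, but the documents say nothing of the kind. Only synopsis-level statistical text and the schedules were available, so a fuller statistical section, if there is one, could not be checked.

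**Conclusion.** The point holds in a limited form. One objective covers two responses that arise in different people, and the planned groupings do not separate those people although the baseline value that does so is collected. Single-cohort summaries can dilute induction heavily: in the illustration the GMFR runs from 4.0 down to 1.32 as the Ad5-positive share goes from 50% to 90%, and the interval excludes 1 in about 72% down to 5% of cohorts of 10. The all-cohort summary would usually register a rise (about 100% down to 55%), but its mean alone could not show whether a few participants rose a lot or all rose a little.

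The size rests wholly on assumed prevalence, fold rise, SD and zero enhancement, and on GMFR being the statistic used. That Ad5-negatives will be a minority is itself only an inference from the Rationale. This is a minor, optional improvement to an exploratory endpoint. It does not undermine the trial's safety or primary immunogenicity conclusions.

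**What to change.** Add one table to the planned summaries, by Ad5 serostatus on Day 1, with the assay cut-off stated in advance:

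- **Baseline Ad5-negative (induction):** GMFR and percentage becoming Ad5-positive, with 95% CIs.
- **Baseline Ad5-positive (enhancement):** GMFR and percentage with at least a fourfold rise, with 95% CIs.

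Present it pooled over all cohorts, and separately for Cohorts 1-2 and Cohorts 3-6. Note beside it that these two sets differ not only in number of doses but also in route and in SARS-CoV-2 serostatus at entry, so a difference between them cannot be put down to any one of these. Plot or list individual Ad5 values by cohort, marked by baseline status. Say which summary will be used for Ad5 T-cell activity, since a fold rise in titre does not carry over to it automatically.

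The cost is some SAP wording and one table; no new sample or visit is needed to split by serostatus. The drawback is small cells, with about 4 and 8 negatives in the two sets at 80% positive, so the table should be labelled descriptive and single cohorts left to the listing.

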
Primary
 
Safety: To determine the safety and reactogenicity of the hAd5-S-Fusion+N-ETSD vaccine at two dose levels for subcutaneous administration, and for sublingual and intranasal dosing.
 
Immunogenicity: To determine immunogenicity of hAd5-S-Fusion+N-ETSD as determined by changes in humoral response.
	
Safety:
 
 • Incidence of MAAEs and SAEs through 1 week post final vaccine administration • Incidence and severity of solicited local reactogenicity AEs through 1 week post final vaccine administration • Incidence and severity of solicited systemic reactogenicity AEs through 1 week post final vaccine administration • Incidence and severity of unsolicited AEs through 1 week post final vaccine administration • Incidence of MAAEs and SAEs through 30 days and 6 months post final vaccine administration • Incidence and severity of unsolicited AEs through 30 days and 6 months post final vaccine administration • Incidence of abnormal changes of laboratory safety examinations • Changes in vital signs 
Immunogenicity: Timing per Schedule of Events
 
 • GMFR in IgG titer to SARS-CoV-2 S, RBD and N. • GMT of S-specific, RBD-specific, and N-specific antibodies against 2019 novel coronavirus tested by ELISA in serum . • Percentage of participants who seroconverted (defined as 4-fold change in antibody titer relative to baseline) . • GMFR in neutralizing antibody .

	
 • GMT of neutralizing antibody . • Seroconversion rate of neutralizing antibody (defined as 4-fold change in antibody titer relative to baseline) .
Secondary	
Safety: 
 • Ascertainment of HIV infections in vaccine recipients through 12 months post final vaccine administration 	Safety: 
 • New HIV infections in vaccine recipients by either two locally approved rapid antibody tests or by ELISA, conducted per Schedule of Events through 12 months post final vaccine administration
Exploratory	

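### Cohorts 3-6 are meant to compare booster routes, but no between-cohort estimate or baseline-titre adjustment is planned, and only Cohorts 3 and 4 share a planned total dose

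*Combined protocol and SAP*

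**What the plan says.** The aim appears in the rationale and again under Study Design: seropositive participants are enrolled in Cohorts 3-6 to "compare the effect of route of administration on the efficacy (and magnitude thereof), reactogenicity and safety of the boosting effect".

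Statistical Methods states: "Descriptive statistics will be presented for all study endpoints by individual cohort, pooled by dose level, and for all cohorts combined". For titres, "GMFRs and GMTs and their associated 95% confidence intervals (CIs) will be computed by exponentiation of the corresponding log-transformed means and 95% CIs"; seroconversion gets a Clopper-Pearson interval. All of these are one-sample summaries.

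Baseline does enter the endpoints. The primary immunogenicity list includes "GMFR in IgG titer to SARS-CoV-2 S, RBD and N", the same measure for neutralising antibody, and seroconversion "defined as 4-fold change in antibody titer relative to baseline". Footnote g of the Schedule of Events secures the baseline value: "Sample collection at vaccination visits should occur prior to vaccine administration". The mucosal endpoint, which is exploratory, is worded without a fold rise: "Mucosal Immunogenicity as assessed by GMT of IgA antibody levels to SARS CoV-2 S protein, RBD and N protein".

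The cohort table gives single-day regimens of SC 1×10^11 VP (Cohort 3), SL 1×10^11 VP (Cohort 4), SC plus SL at 1×10^11 VP each (Cohort 5) and IN 2×10^10 VP per nostril (Cohort 6). Its footnote adds: "Total IN dose is given is 4×10^{10} VP as vaccine will be administered into both nostrils". If there are safety concerns, SC dosing in Cohorts 3 and 5 falls to 5×10^10 VP. Each cohort opens after the Safety Review Committee has reviewed the one before. The serology criterion for Cohorts 3-6 is a positive result on a locally approved assay, with no titre band.

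**The concern.** A comparison is announced, but the analysis stops at four separate columns of results, and readers will do the comparing themselves. Three things would then be mixed together.

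- **Baseline titre.** Previously infected people can enter at very different titres. Measuring each person against their own baseline does not make cohorts comparable when the rise itself depends on the starting titre.
- **Enrolment period.** The cohorts fill one after another during a pandemic, so time since infection and circulating virus may differ between them.
- **Total dose.** Most pairs of cohorts differ in total viral particles as well as route.

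At stake is which booster route is carried forward. A route could look better because its cohort started lower (on GMFR), started higher (on GMT) or received more vaccine.

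**Working it through.** **1. Total dose (cohort table).** Cohort 6: 2 nostrils × 2×10^10 = 4×10^10 VP, which reproduces the footnote. Cohort 5: 1×10^11 + 1×10^11 = 2×10^11 VP. Cohorts 3 and 4: 1×10^11 VP each. Largest over smallest: 2×10^11 / 4×10^10 = 5.0.

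Of the six pairs, only 3 versus 4 is equal. With the SC fallback the totals for Cohorts 3 to 6 become 5×10^10, 1×10^11, 1.5×10^11 and 4×10^10 VP. All six pairs then differ, and the range is 1.5×10^11 / 4×10^10 = 3.75.

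**2. Direction of the baseline effect.** Write post-dose log10 titre as a + b × baseline log10 titre, with no route effect. If two cohorts differ by d in mean baseline, the log GMT ratio is b·d and the log GMFR ratio is (b − 1)·d. For 0 < b < 1 these have opposite signs: GMT favours the high-baseline cohort and GMFR the low-baseline one.

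**3. Illustrative size.** The documents give no SD or slope, so both are assumed: baseline SD 0.6 log10 and b = 0.5. From the documents, n = 10 per cohort.

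- SE of d = 0.6 × √(2/10) = 0.268 log10.
- Median |d| = 0.674 × 0.268 = 0.181 (1.5-fold); 95% limit = 1.96 × 0.268 = 0.526 (3.4-fold).
- At b = 0.5 the distortion is the same size for GMT and GMFR: 10^(0.5 × 0.181) = 1.23 at the median and 10^(0.5 × 0.526) = 1.83 at the 95% limit.

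For other slopes:

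| Slope b | GMT, median / 95% limit | GMFR, median / 95% limit |
|---|---|---|
| 0.3 | 1.13 / 1.44 | 1.34 / 2.33 |
| 0.5 | 1.23 / 1.83 | 1.23 / 1.83 |
| 0.7 | 1.34 / 2.33 | 1.13 / 1.44 |

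These figures are for chance alone. Any systematic shift from sequential enrolment is extra. For example, a 2-fold baseline difference at b = 0.5 gives a GMFR ratio of 2^(−0.5) = 0.71 and a GMT ratio of 2^0.5 = 1.41, with no route effect.

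**4. What an adjusted ratio could deliver.** Add an assumed post-dose SD of 0.5 log10. Baseline SD 0.6 and slope 0.5 then imply a correlation of 0.5 × 0.6 / 0.5 = 0.6.

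- Change-score SD = √(0.36 + 0.25 − 2 × 0.6 × 0.6 × 0.5) = 0.5, the same as the post-dose SD.
- Residual SD after adjustment = 0.5 × √(1 − 0.36) = 0.4, which is 20% smaller than either.
- Unadjusted two-cohort 95% CI: ×/÷ 10^(2.101 × 0.5 × √0.2) = 2.95.
- Adjusted: ×/÷ 10^(2.110 × 0.4 × √0.2) = 2.38, slightly wider once the cost of estimating the slope is counted.

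Either interval is too wide to rank routes. With SD 0.5, an unadjusted two-sided 5% t-test at 10 per cohort has about 25% power for a true 2-fold ratio.

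**The case against.** **The plan already uses baseline.** This is correct. GMFR and seroconversion are both relative to each participant's own pre-dose value, so a reader who infers that the plan ignores baseline titre goes too far. What is absent is adjustment when cohorts are set against each other.

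**GMT and GMFR bracket the answer.** For a slope between 0 and 1 the adjusted ratio lies between the two raw ratios, and both can be derived from the planned tables. That is a fair point, but two ratios that err in opposite directions supply neither the adjusted estimate nor its interval.

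**Chance imbalance is already inside an unadjusted CI.** This is true of an interval for a between-cohort ratio, but none is planned. Nor need imbalance between sequential cohorts be due to chance.

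**Side-by-side description is a fair reading of 'compare' in an open-label phase 1b trial.** This has weight. The comparison does not appear in the objectives table, and the doses are disclosed. It limits the severity. A descriptive trial can still report a ratio with an interval.

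**Salivary IgA is exploratory and Day 1 saliva is collected.** A Day 1 GMT will therefore be available, and on complete pairs the ratio of the GMTs equals the GMFR. Its paired interval cannot be recovered from two separate GMTs, however.

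**The statistical text supplied is at synopsis level.** It refers to a table that is not included, so a fuller section may exist. The finding concerns the text supplied.

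**Conclusion.** The point holds as a recommended change, not a fatal flaw. Route comparison is a declared reason for enrolling Cohorts 3-6, and the supplied text plans no between-cohort estimate and no baseline adjustment for one. The five-fold dose range and the count of five unequal pairs are exact at planned doses. The 1.2-fold and 1.8-fold distortions are illustrations that rest on an assumed SD of 0.6 log10 and slope of 0.5; the documents supply neither.

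Two stronger readings are not supported. A reader might infer that dose confounds every route contrast, but Cohorts 3 and 4 have equal planned total dose unless the SC fallback is used. A reader might also infer that the trial can say nothing about route. It can give estimates with wide intervals, and for Cohort 3 versus 4 at equal planned dose, though still non-randomised. Nor should the remedy be oversold: ANCOVA removes only the part of the imbalance carried by Day 1 titre.

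**What to change.** - For Cohorts 3-6, pre-specify one ANCOVA per antibody of log titre at 30 days post dose (Day 31 in the Schedule) on cohort and log Day 1 titre. Report baseline-adjusted GMT ratios with 95% CIs, as estimation and not as a ranking of routes.
- For salivary IgA, report fold rise from Day 1 and the same adjusted ratio.
- Leave Cohorts 1 and 2 out of this model: they were seronegative at entry, so baseline antibody probably varies little.
- State in the design and statistical text that all comparisons among Cohorts 3-6 are descriptive and non-randomised; that Cohort 3 versus 4 is the only equal-dose route contrast, and only if the SC fallback is not used; that comparisons involving Cohorts 5 or 6 are of regimens (route plus total dose); and that baseline adjustment does not remove calendar-time or dose differences.

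The cost is one extra model and a narrower route claim. No dose, visit or sample changes, because the Day 1 and Day 31 serum and saliva are already scheduled.
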